6.5. Dose Modification

6.5.1. Dose Modification of Dupilumab/Placebo

Dose modification of dupilumab/placebo for an individual subject is not allowed.

6.5.2. Premature Discontinuation of Investigational Agent

Study therapy (dupilumab/placebo and/or milk OIT) will be prematurely discontinued for any participant if:

- the investigator believes that the study treatment is no longer in the best interest of the participant
- the participant has anaphylactic reaction or other severe systemic reaction to dupilumab per investigator decision
- the participant acquires an infection that is opportunistic, such as active tuberculosis and other infections whose nature or course may suggest an immuno-compromised status
- the participant acquires a diagnosis of a malignancy during the study
- the participant demonstrates evidence of pregnancy
- the participant receives treatment with any prohibited concomitant medication or procedure

Study therapy (milk OIT) will be prematurely discontinued for any participant under circumstance that include, but are not limited to, the following:

- poor control or persistent activation of secondary atopic disease (e.g. AD, asthma)
- circumstances (e.g. concurrent illness, such as gastroenteritis, or non-compliance) develop requiring missed allergen OIT dosing of ≥ 7 consecutive days
- non-adherence with home OIT dosing protocol (excessive missed days per investigator discretion) without consulting with study staff
- the investigator believes that the study treatment is no longer in the best interest of the participant

A decision to discontinue study drug should be discussed with the study Sponsor. The investigator may suspend study treatment at any time if the urgency of the situation requires immediate action and if this is determined to be in the subject's best interest. However, the Sponsor should be contacted as soon as possible in any case of study drug discontinuation.

Subjects who permanently discontinue from study drug and who *do not withdraw from the study* will be asked to return to the clinic for all remaining study visits per the visit schedule.

Subjects who permanently discontinue from study drug and who opt to withdraw from the study will be asked to complete an Early Termination visit within 14 days of the last dose of the study drug. Assessments at this visit may include a blood draw for immunological parameters and translational/mechanistic studies; stool/saliva sampling; and physical exam, spiroometry (as able), and skin testing.

7. OTHER MEDICATIONS

7.1. Concomitant Medications

Any treatment administered from the time of the first dose of study drug to the final study visit will be considered concomitant medication. This includes medications that were started before the first dose of study drug and are ongoing during the study.

7.1.1. Protocol-Mandated Concomitant Medications

There are no protocol-mandated concomitant or prophylactic medication(s) to be administered during the study.

7.1.2. Permitted Concomitant Medications

All subjects may continue their usual medications, including those taken for asthma, allergic rhinitis, and AD, during the study. Participants may dose with an antihistamine or antacid prior to their home dose; however, they must be able to discontinue antihistamines for at least 5 half-lives prior to the initial day of escalation, skin prick testing, in-clinic OIT updosing, and all oral food challenges. Usual topical steroid use is permitted at the time of skin testing. Systemic (oral, IV, IM) steroid use longer than 7 days at one time or longer than 3 weeks (21 days) duration each year is not allowed. Up-dosing will not occur within 3 days of systemic steroid use. PPI use will be allowed as detailed under *Reactions to OIT During Combination Therapy or Washout Phase*.

7.1.3. Prohibited Medications and Procedures

Participants will be removed from the trial if any of the following medications are used:

- An investigational drug (other than dupilumab as part of the study)
- Immunomodulating biologic agents, including anti-IgE
- Oral antihistamines (within five half lives), beta-agonists (within 12 hours), theophylline (within 12 hours), and cromolyn (within 12 hours) prior to the initial day of escalation, skin prick testing, in-clinic OIT updosing, and all oral food challenges
- Systemic (oral, IV, IM) corticosteroids used for any greater than 7 days at one time or longer than a total of 3 weeks (21 days) duration each year for asthma. If used, subjects must not be up-dosed until at least 3 days after ceasing the administration of oral steroids
- β-blockers

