5.4. Risk of Other Protocol-Specified Medications

Epinephrine Injection

Common side effects of epinephrine when used properly include anxiety; apprehensiveness; restlessness; tremor; weakness; dizziness; sweating; palpitations; pallor; nausea and vomiting; headache; and/or respiratory difficulties. Heart problems and stroke, particularly in the elderly

and people with health problems, have been seen. Rare cases of serious skin and soft tissue infections have been reported at the injection site following epinephrine injection in the thigh.

It is very important to use proper techniques when giving epinephrine to avoid injury to the person administering the epinephrine or to the person receiving the injection. In addition to the common side effects above, accidental injection into the finger, hand or foot may result in loss of blood flow to the area causing paleness; coldness; numbness; bruising; bleeding; redness; or damage to the bones. Epinephrine should not be injected into the buttocks and has resulted in cases of gas gangrene.

Anti-histamines

H1 receptor antagonists (e.g., cetirizine, loratadine, fexofenadine) will be used orally according to manufacturer's instructions approximately one hour prior to each food allergen dose at home. The risks of these medications include:

- Central nervous system: Headache, fatigue, somnolence, drowsiness, insomnia, sleep disorders, dizziness, muscle pain
- Gastrointestinal: Diarrhea, nausea, vomiting, dyspepsia, abdominal pain, dry mouth
- Neuromuscular & skeletal: Myalgia, back pain, pain in extremities
- Hypersensitivity reactions (anaphylaxis, angioedema, chest tightness, dyspnea, flushing, pruritus, rash, urticaria)

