7.2. Rescue Medications

Rescue medications for any clinically significant reaction will include Epinephrine auto-injectors (dosed according to product insert), antihistamine class of medications (dosed according to weight of subject and according to package guidelines), and inhaler medications (short-acting beta agonist class of medications). The investigators will use their clinical judgment to apply these medications in an event of a reaction. In addition, all rescue medications are available within immediate reach in each room of the research clinic while dosing occurs. Rescue medications can be given IV, IO, IM, by inhalation, and/or by oral route as dictated by the research clinician. For home dosing, the same class of medications will be available and all the

subjects/parents/guardians will receive detailed instructions and education on the use of these reaction medications.

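### Section 7.1.3 orders removal for antihistamine or beta-agonist use shortly before a procedure, without a rescue exemption or postponement, and Sections 5.4, 6.5.2, 8.3 and 10.1 do not agree with it

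*Combined protocol and SAP*

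**What the plan says.** - **Section 7.1.3** opens with "Participants will be removed from the trial if any of the following medications are used". One bullet reads "Oral antihistamines (within five half lives), beta-agonists (within 12 hours), theophylline (within 12 hours), and cromolyn (within 12 hours", and ties these windows to four procedures: the initial escalation, skin prick testing, in-clinic up-dosing and every food challenge. The steroid bullet sets duration limits and then adds a delay: "If used, subjects must not be up-dosed until at least 3 days after ceasing the administration of oral steroids".
- **Section 7.2** names antihistamines and "inhaler medications (short-acting beta agonist class of medications" as rescue treatment, allows the oral and inhaled routes, and adds "For home dosing, the same class of medications will be available".
- **Section 6.5.2** lists, as a reason to stop study therapy, that "the participant receives treatment with any prohibited concomitant medication or procedure". Those who stop the drug but stay in the study "will be asked to return to the clinic for all remaining study visits per the visit schedule".
- **Section 10.1** says participants may be terminated if started on a prohibited medication for which the prescriber has no alternative.
- **Section 5.4** says "H1 receptor antagonists (e.g., cetirizine, loratadine, fexofenadine) will be used orally", about an hour before each home dose. Section 7.1.1 says no concomitant or prophylactic medication is mandated. Section 7.1.2 makes home premedication optional and requires a stop of at least five half-lives before the same four procedures.
- **Section 8.3** asks participants to hold prophylactic antihistamines on the day of in-clinic dosing. After a treated reaction it requires at least 48 hours between the two challenges, at week 18 and again at week 24.
- **Section 13.5.1** scores a participant as a non-responder after withdrawal, and at any time point with missing data.

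**The concern.** The rescue drugs are in the same classes as the drugs that trigger removal. A participant who treats a home reaction the evening before an up-dosing visit, as trained to do, is inside the window the next morning. Section 7.1.3 tells the site to remove that participant. Section 6.5.2 tells it to stop therapy but keep the participant attending, and 10.1 leaves termination to discretion. Two sites could handle the same event differently.

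The outcome matters for the analysis. A participant removed before week 18 has no challenge and counts as a failure on the primary endpoint. One kept under 6.5.2 can still have the week-18 challenge.

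Separately, a participant or site that follows only 5.4 and 8.3 can arrive at up-dosing with an antihistamine still inside the washout that 7.1.2 and 7.1.3 require. That is a safety and measurement matter as well as a compliance one.

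**Working it through.** **1. Consequences side by side.**

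| Section | Trigger | Consequence |
|---|---|---|
| 7.1.3 | One of the four drug classes inside the window before a procedure | Removal from the trial |
| 6.5.2 | Any prohibited medication | Study therapy stops; remaining visits continue unless the participant withdraws |
| 10.1 | Started on a prohibited medication with no alternative | May be terminated |

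Neither 7.1.3 nor 7.2 mentions rescue use as an exception. Section 7.1.3 builds a delay into its steroid bullet but not into the antihistamine and beta-agonist bullet.

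**2. Same-day hold against the five-half-life washout.** The documents give no half-lives, so the check finds the longest half-life that a given gap clears: gap divided by 5.

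Inputs: premedication about 1 h before the home dose (5.4); home doses 24 ± 2 h apart (8.3); clinic dose assumed to fall at the usual dosing time.

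- Gap = 1 + 24 = 25 h, range 1 + 22 = 23 h to 1 + 26 = 27 h.
- Longest half-life cleared = 25/5 = 5.0 h, range 23/5 = 4.6 h to 27/5 = 5.4 h.

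This applies to a participant who premedicates under 5.4 and observes only the 8.3 hold, at the up-dosing visits V5 to V10 (six) and V12 and V13 (two), eight in all. The hold is written for in-clinic dosing, so challenge days rest on 7.1.2 and 7.1.3 alone.

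**3. Challenge spacing after a treated reaction.**

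- Minimum of 48 h: 48/5 = 9.6 h.
- V11b at most 7 days after V11a: 168/5 = 33.6 h.
- V14b at most 10 days after V14a: 240/5 = 48 h.
- Beta-agonists: 48 h exceeds the 12 h window, so the spacing rule is enough for them.

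Over an assumed half-life range of 4 to 30 h, five half-lives run from 20 to 150 h. Half-lives of 4 and 8 h need 20 and 40 h and fit inside 48 h. Half-lives of 12, 15, 20, 24 and 30 h need 60, 75, 100, 120 and 150 h; they do not fit 48 h but all fit 168 h.

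**4. Does postponement fit the windows?** Visits may be 5 days late. If premedication stops after the last dose before the nominal day, the gap becomes 25 + 5 × 24 = 145 h, and 145/5 = 29 h. If the participant goes on premedicating daily during the delay, the gap falls back to about 25 h, so the delay works only together with the stop that 7.1.2 requires. Rescue given in clinic at one up-dosing visit is rarely an issue for the next, at least 9 days later: 216/5 = 43.2 h.

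**5. Route to the endpoint.** Removal before week 18 makes the participant a non-responder on the primary endpoint. A treated reaction at V11a will ordinarily be to milk, because screening excludes those who react to oat. The week-18 milk result is then already observed, and V11b is the placebo challenge. Removal at that point would instead make the participant a non-responder at week 24.

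**The case against.** The strongest reply is that 7.1.3 prohibits a drug within a set time before a procedure. Rescue use alone does not meet that condition; it is met only if the procedure then goes ahead inside the window. A site that delays the visit has no in-window use and nobody to remove. The means are in place: visits may move by 5 days, 8.3 has the diary reviewed before up-dosing, V11b and V14b have 7 and 10 days, and 12.4 lets deviations be considered individually. Section 7.1.2 states the washout outright, 8.3 tells participants to respect the protocol's prohibitions for their other medicines, and 48 hours is a minimum. Section 5.4 describes risks, whereas 7.1 is the operative text. The Manual of Procedures, which is not among the documents, may settle the rest.

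Most of this stands, and it limits the point to one of consistency. It does not remove it. Section 7.1.3 names removal and is silent on postponement for these drugs, three sections give three consequences, and 5.4 still contradicts 7.1.1 and 7.1.2.

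A reader might infer that any rescue use leads to removal, or that the 48-hour rule makes compliance impossible. The text supports neither. A reader might also infer a biased primary comparison, since Section 2.1 hypothesizes fewer adverse events on dupilumab and so perhaps fewer rescue-related removals in that arm. The documents give no rate of in-window use in either arm, and sites can avoid removal by delaying, so neither a bias nor its direction follows.

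**Conclusion.** The inconsistency is real and minor. Section 7.1.3 prescribes removal without a rescue exemption or a postponement option; 6.5.2 and 10.1 prescribe something else; 5.4 conflicts with 7.1.1 and 7.1.2.

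The 8.3 hold falls short of the required washout for half-lives above about 5 h, assuming the premedication and dosing times in 5.4 and 8.3 and a clinic dose at the usual hour. The 48-hour spacing falls short only for antihistamines with half-lives above 9.6 h, and mostly once the milk result is known.

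No effect on the primary endpoint can be sized: the documents give no half-lives and no frequency of in-window use.

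**What to change.** - **7.1.3:** for oral antihistamines, beta-agonists, theophylline and cromolyn used inside the window, replace removal with postponement of the initial escalation, skin prick test, up-dosing or challenge within the visit window. State that rescue use under 7.2 is not a reason for removal. Send cases that cannot fit the window to 12.4; a 30 h half-life at an up-dosing visit is an example, needing 150 h against 145 h.
- **6.5.2 and 10.1:** except this in-window use from their prohibited-medication criteria, so that all three sections give one consequence.
- **5.4:** change the premedication sentence from will to may.
- **8.3:** replace the same-day antihistamine hold with the five-half-life washout for V4 to V10, V12 and V13, and apply the same washout to the spacing of the week-18 and week-24 challenges.

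The cost is wording in five sections and occasional delays inside the existing windows: up to 5 days for a visit, V11b up to 7 days after V11a, V14b up to 10 days after V14a. Sample size and the primary analysis do not change.

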7.2. Rescue Medications

Rescue medications for any clinically significant reaction will include Epinephrine auto-injectors (dosed according to product insert), antihistamine class of medications (dosed according to weight of subject and according to package guidelines), and inhaler medications (short-acting beta agonist class of medications). The investigators will use their clinical judgment to apply these medications in an event of a reaction. In addition, all rescue medications are available within immediate reach in each room of the research clinic while dosing occurs. Rescue medications can be given IV, IO, IM, by inhalation, and/or by oral route as dictated by the research clinician. For home dosing, the same class of medications will be available and all the

subjects/parents/guardians will receive detailed instructions and education on the use of these reaction medications.

8. STUDY VISITS

8.1. Enrollment

The research study will be explained in lay terms to each potential research participant. The potential participant or guardian of a child participant will sign an informed consent form before undergoing any study procedures, with those aged 7 years or older completing an assent. Once the informed consent/assent has been signed, the participant is considered enrolled in the study. The purpose of enrollment is to complete the screening phase to determine eligibility. The participant will then be assigned a unique participant number after signing the informed consent/assent document(s).

8.2. Screening/Baseline Visits (V1)

The purpose of the screening period is to confirm eligibility to continue in the study. After obtaining informed consent/assent, subjects will be assessed for eligibility at a screening visit. Procedures for the screening visit may be spread over one to three separate days; these days do not need to be consecutive and can be spread out over the course of the entire screening window. All assessments must be completed no more than 6 months preceding initiation dupilumab/placebo (Visit 2, week 0), excluding the milk-specific IgE value which may be taken from the previous 12 months if needed to establish eligibility. Baseline/screening visit procedures following requirements below but conducted under a different protocol within the past 6 months (or 12 months for milk-specific IgE) prior to Visit 2 can be used towards this study. Visit 1 may occur on the same day as Visit 2, but must be completed prior to any Visit 2 procedure taking place.

The following procedures, assessments, and laboratory measures will be conducted to determine participant eligibility and collect baseline data:

- Consent and assent (conducted prior to any screening or study procedure)
- Medical history, including review of all food allergies
- Physical assessment
- Documentation of con meds and AEs
- Epinephrine auto-injector training with Food Allergy & Anaphylaxis Emergency Care Plan
- SPT to cow's milk (only if needed to determine eligibility)
- Lung function (spirometry, or peak flow if spirometry not available, applicable, or able to be performed reliably by the participant). If spirometry and peak flow are both unable to be completed, defer to clinician judgment
- Urine pregnancy test in women of childbearing potential (WOCBP)

Any of the above items may be repeated within the 6 months preceding initiation of study treatment if warranted, in the opinion of the investigator, by changes in the subject's clinical status. After all other eligibility criteria have been met, DBPCFCs to a cumulative 444 mg of milk and placebo (oat)

Double-Blind Placebo-Controlled Food Challenge (DBPCFC) at Screening

Participants meeting all other eligibility criteria will undergo DBPCFC to cow's milk protein and oat (placebo) during screening to confirm an allergy to milk. Randomization of the placebo and

milk challenge order and preparation of the challenge materials will be performed by trained unblinded study personnel.

All food challenges will be performed under clinician supervision. Before each challenge, the subject will have a physical examination and lung function assessment conducted to ensure it is safe and appropriate to conduct the challenge. Each challenge will be supervised by a trained clinician who is blinded to the testing material. The screening DBPCFC will consist of 6 doses of milk protein given every 15-30 minutes in increasing amounts up to a cumulative total of 444 mg protein. The doses will be 1 mg, 3 mg, 10 mg, 30 mg, 100 mg, and 300 mg (see **Table 2**). The other challenge will consist of placebo material given also in 6 matching doses. Vital signs will be assessed every 15 minutes. If the study team suspects a reaction may be developing, they may exercise their clinical judgment to separate doses by up to an additional 30 minutes (one hour maximum between doses). The food challenge will be stopped and appropriately treated in the occurrence of two or more objective Grade 1 (Mild) reactions involving two or more organ systems; OR a persistent Grade 1 (Mild) reaction; OR any reaction of Grade 2 (Moderate) or higher severity. After the last dose of each DBPCFC, the subject will be monitored for 2 hours and then discharged from the clinic. Subjects will be considered to have tolerated the DBPCFC and excluded from the study if they do not experience any of the dose-limiting symptom criteria detailed above and tolerate all doses of the challenge.

Table 2. Dosing Regimen for DBPCFCs at Screening and Weeks 18/24

Dose #	Screening Milk OIT/Placebo Dose (mg protein)	Weeks 18/24 Milk OIT/Placebo Dose (mg protein)
1	1	10
2	3	30
3	10	100
4	30	300
5	100	600
6	300	1000
7	NA	2000

